5.1. Inclusion Criteria

Patients are eligible to be included in the study only if they meet all of the following criteria prior to randomization as indicated below:

Type of Patient and Disease Characteristics

- [1] Present with chronic plaque psoriasis based on a diagnosis of chronic plaque psoriasis for at least 6 months before baseline (Week 0; Visit 2), as determined by the investigator
- [2] Are candidates for phototherapy and/or systemic therapy
- [3] Have an overall sPGA ≥ 3 at screening (Visit 1) and at baseline (Week 0, Visit 2)
- [4] Have sPGA of Genitalia ≥ 3 at screening (Visit 1) and at baseline (Week 0, Visit 2)
- [5] Have BSA involvement of $\geq 1\%$ at screening (Visit 1) and at baseline (Week 0, Visit 2)

(Note: The majority of patients will be required to have BSA involvement $\geq 10\%$ and up to approximately 40% of patients will be allowed to have BSA involvement of 1 to $<10\%$. Enrollment will be closely monitored, and enrollment in this lower BSA subpopulation will be stopped if a maximum of 40% is reached.)
- [6] Have confirmation of plaque psoriasis in a nongenital area at screening (Visit 1) and baseline (Week 0, Visit 2)

- [7] Have failed to respond to, or are intolerant of, at least 1 topical therapy (corticosteroids, calcineurin inhibitors and/or vitamin D analogs) used for treatment of psoriasis affecting the genital area

Patient Characteristics

- [8] Are male or female patients of 18 years or older
- [9] Must agree to use reliable method of birth control:
- If a male patient, agree to use a reliable method of birth control during the study and for at least 12 weeks following the last dose of investigational product. Examples of reliable methods include abstinence, vasectomy, and male condom with spermicide.

OR

- If a female patient of childbearing potential, must test negative for pregnancy and agree to use a reliable method of birth control during the study and for at least 12 weeks following the last dose of investigational product. Methods of contraception considered acceptable include abstinence, oral contraceptives, contraceptive patch, intrauterine device, vaginal ring, diaphragm with contraceptive gel, or condom with contraceptive gel.

OR

- For nonchildbearing potential female patients, patients must be:

Women who have had surgical sterilization (hysterectomy, bilateral oophorectomy, or tubal ligation)

OR

Women who are ≥ 60 years of age

OR

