8.1.2. Secondary Efficacy Assessments

8.1.2.1. Clinician Reported Assessments

8.1.2.1.1. Modified Genital Psoriasis Area and Severity Index

The mGPASI was adapted from the standard PASI by Bissonnette et al. (2008) and Ryan et al. (2015) for use in male and female genital psoriasis patients. The measure is the clinician's determination of the patient's psoriasis severity in the genital region (labia majora, labia minora, and perineum in females; penis, scrotum, and perineum in males) at a given time point yielding an overall score of 0 for no psoriasis to 72 for the most severe disease. The scoring index incorporates the degree of erythema, induration, and scaling of the genital plaques as well as erosion, fissure, and/or ulcer as a product of the genital area involved. Severity is rated for each characteristic on a 0 to 4 scale (0 for no involvement up to 4 for severe involvement including erosion, fissure, and/or ulcer). The area of involvement for the entire genital area, excluding the inguinal area, is graded on a 0 to 6 scale (0 for no involvement; up to 6 for 90% to 100% involvement).

8.1.2.1.2. (Overall) static Physician Global Assessment

The sPGA is the physician's determination of the patient's psoriasis lesions overall at a given time point. The sPGA is recommended as an endpoint to assess efficacy in the treatment of psoriasis (EMA 2004). Overall, lesions are categorized by descriptions for induration, erythema, and scaling. For the analysis of responses, the patient's psoriasis is assessed as clear (0), minimal (1), mild (2), moderate (3), severe (4), or very severe (5).

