mGPASI	The Modified Genital Psoriasis Area and Severity Index (mGPASI) measure is the clinician’s determination of the patient’s psoriasis severity in the genital region (labia majora, labia minora, and perineum in females; penis, scrotum, and perineum in males) at a given time point yielding an overall score of 0 for no psoriasis to 72 for the most severe disease. The scoring index incorporates the degree of erythema (or redness (R)), induration (or thickness (T)), and scaling (S) of the genital plaques as well as erosion, fissure, and/or ulcer as a product of the genital area involved. Severity is rated for each	mGPASI score	The composite mGPASI score is calculated by summing the individual severity scores for erythema, induration and scaling / erosion, fissure, and/or ulcer, and then multiplying the sum by the area-of-involvement score as follows: $\text{mGPASI} = (R + T + S)A$ Where, R = Redness score T = Thickness score S = Scaling / Erosion, fissure and/or ulcer score A = numerical value translation of % area of psoriatic involvement scores mGPASI scores are treated as a continuous score.	If any individual component score is missing, then the mGPASI score will not be calculated, and hence mGPASI score will be missing

Measure	Description	Variable	Derivation	Imputation Approach if Components are Missing
	characteristic on a 0 to 4 scale (0 for no involvement up to 4 for severe involvement including erosion, fissure, and/or ulcer). 0 = none 1 = slight 2 = moderate 3 = severe 4 = very severe The area of involvement for the entire genital area, excluding the inguinal area, is graded on a 0 to 6 scale (0 for no involvement; up to 6 for 90% to 100% involvement). 0 = 0% (clear) 1 = 1% – 9% 2 = 10% – 29% 3 = 30% – 49% 4 = 50% – 69% 5 = 70% – 89% 6 = 90% – 100%	Change from baseline in mGPASI	$\text{Change from baseline} = \text{Observed mGPASI} - \text{Baseline mGPASI}$ A negative change indicates improvement and a positive change indicates deterioration of the condition.	Missing if baseline mGPASI or observed mGPASI value is missing

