Test-retest reliability has been emphasized by the FDA as an important aspect of reliability in the FDA PRO Guidance (FDA 2009). Test-retest reliability reflects the ability of the instrument to give reproducible results when the clinical state is stable and indicates the degree to which a measure produces consistent results over several administrations. Test-retest reliability will be examined for: 1) GPSS items and total score, 2) GPSIS subscales, 3) SFQ item 2, and 4) sPGA of Genitalia prior to the first study drug injection. Stable subjects will be defined in two ways: 1) patients who had the same rating on the overall sPGA at screening and baseline visit, and 2) patients whose change in mGPASI score at screening and baseline visit <0.5 SD of mGPASI at baseline. For daily diary, patients are required to enter start entering GPSS at least 14 days prior to the first injection. The test score will be the average of 8 to 14 days prior to the first injection; whereas the re-test score will be the average of 1 to 7 days prior to the first injection, the same as baseline score. When there are less than 4 non-missing assessments within respective window, the search window will be expanded repeatedly until 4 non-missing assessments are available to compute the average score. Otherwise, the test, or re-test score will be set to missing. For weekly diaries, including GPSIS and SFQ, patients are also required to have 2 assessments collected prior to the first study drug injection in order to be included in the analysis.

Test-retest reliability will be assessed using intra-class correlations coefficients (ICCs) and paired sample t-tests among stable patients only.

Intra-class correlations coefficients range from 0 to 1.0, with higher scores indicating a more stable instrument. The hypothesis is that there will be no significant differences in scale scores when there is no change in disease status. Given that the majority of evaluated measures are single-item scales, a threshold of >0.60 will be supportive of test-retest based on the lower limit provided by Devellis (1991).

6.20.1.2.5.3. Construct Validity

6.20.1.2.5.3.1. Convergent and Divergent Validity

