Additionally, the RD of the change in GPSS item and total score and the subscale of GPSIS, Sexual Activity Avoidance Subscale, from baseline to Week 12 will be derived by anchoring them on sPGA of Genitalia (0,1) at Week 12. The correlation between change in each measure and change in sPGA of Genitalia from baseline to Week 12 will first be computed to assess the strength of the anchor. A logistic model will then be utilized by regressing the change in each measure on the anchor. Concordance index will be computed to assess the adequacy of the model fitting. Predictive statistics, including sensitivity, specificity, positive predictive value, negative predictive value and Youden index, will be presented at each possible change of value for each measure.

A RD will be derived for sPGA of Genitalia and the subscale of GPSIS, Sexual Activity Avoidance Subscale at Week 12 by anchoring on 1) PatGA-Genitalia (0,1) at Week 12 as an anchor. Correlation between each measure and anchor variable will be first assessed prior to constructing the logistic model.

A RD will be derived for SFQ Item #2 and GPSIS subscales comprising the change of score and static score at Week 12 using PatGA-Genital (0,1) and sPGA of Genitalia (0,1) at Week 12 as anchors.

6.20.1.2.5.5.2. Distribution-Based Method

For the distribution-based methods, supportive evidence for the RD will be assessed using one standard error of measurement (SEM) and 0.5 SD of the scales of interest at baseline.

Standard of error of measurement has been proposed as a useful distribution-based statistic for evaluating clinically meaningful change in health-related quality of life (HRQL) measures (Wyrwich et al. 1999a; Wyrwich et al. 1999b). The SEM describes the error associated with the measure and is estimated by the baseline standard deviation of the measure multiplied by the square root of one minus its reliability coefficient (ICC from the test-retest assessment).

Previous research suggests that one SEM is roughly associated with a clinically important difference for PRO measures (Wyrwich et al. 1999a; Guyatt et al. 2002). Other research suggests changes (or differences) of 0.20 to 0.30 effect size may be indicative of a minimal important difference (Osoba and King 2005; Revicki et al. 2008).

An alternative distribution-based approach consists of calculating a 0.5 SD of the scales of interest at baseline. It has been suggested that one-half of a standard deviation of a measure

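### The first stability rule for test-retest of the genital scales uses the whole-body sPGA, so a patient whose genital disease changed before dosing can be counted as stable

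*SAP*

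**What the plan says.** SAP 6.20.1.2.5.2 (Test-Retest Reliability) covers GPSS items and total, the GPSIS subscales, SFQ item 2 and sPGA of Genitalia, all before the first injection. It states: "Stable subjects will be defined in two ways". The first is "patients who had the same rating on the overall sPGA at screening and baseline visit". The second is "patients whose change in mGPASI score at screening and baseline visit <0.5 SD of mGPASI at baseline". ICCs and paired t-tests are run in stable patients only, and an ICC above 0.60 counts as supportive. The section does not say whether the two definitions are applied separately or together.

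The two stability measures cover different sites. Protocol 8.1.2.1.2 describes the overall sPGA as rating "psoriasis lesions overall at a given time point". SAP Table RHBQ.6.3 describes the mGPASI as rating "psoriasis severity in the genital region".

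SAP 6.20.1.2.5.5.2 (Distribution-Based Method) multiplies the baseline standard deviation by "the square root of one minus its reliability coefficient (ICC from the test-retest assessment" to obtain the SEM. It does not say which stable set supplies the ICC. SAP 6.20.1.2.5.5 ranks distribution-based evidence as supportive, behind anchor-based methods.

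**The concern.** Test-retest reliability means something only if the condition being measured has not moved between the two occasions. All four instruments concern the genital area, but the first rule checks the whole body. Genital disease may improve or worsen while the body rating stays in the same category. Such a patient enters the stable set, and the real change is booked as measurement error.

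Pre-dose genital change is plausible. Protocol 5.1 criterion [7] requires failure of, or intolerance to, at least one topical therapy used for genital psoriasis. Protocol 5.2 criterion [14] excludes topical psoriasis treatment in the two weeks before baseline, apart from mild corticosteroids on the face or axilla. Screening falls about 7 to 30 days before baseline.

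At stake are the ICC judged against 0.60, the paired t-test, and the SEM, which joins the triangulation of a responder definition.

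**Working it through.** **No figure to reproduce.** The documents give no ICC, SEM, mGPASI SD, or size of the stable set. What follows shows direction and a plausible range. It is not an estimate for this trial.

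**Is a site-matched measure available?** In Protocol Appendix 2, overall sPGA, sPGA of Genitalia and mGPASI are all scheduled at Visits 1 and 2. PatGA-Genital starts at Visit 2, so it cannot define pre-dose stability.

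**From ICC to SEM.** SEM/SD = √(1 − ICC): 0.632 at ICC 0.60, 0.548 at 0.70, 0.500 at 0.75, 0.447 at 0.80.

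**Simple illustration (shares assumed).** Suppose the ICC is 0.80 in truly stable patients, and a fraction f of the set labelled stable changed by 0.8 SD, unrelated to their starting level. Then ICC = 0.80 / (1 + f × 0.64/2).

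- f = 0.15: 0.80/1.048 = 0.76; SEM 0.49 SD against 0.45, about 9% larger.
- f = 0.30: 0.80/1.096 = 0.73; SEM 0.52 SD, about 16% larger.

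Both ICCs stay above 0.60.

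**Simulation (all inputs assumed).** There were 1,000,000 patients per scenario, with a two-way absolute-agreement ICC. Assumed inputs:

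- true reliability 0.7 or 0.8;
- SD of true genital change 0.3, 0.5 or 0.8 of the between-patient SD;
- mean change 0, −0.3 or +0.3;
- mGPASI error SD 0.33;
- correlation 0.3 between overall and genital change;
- overall sPGA categories 1.5 SD wide.

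Results with zero mean change:

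| True reliability | SD of true change | ICC, overall sPGA unchanged | ICC, absolute mGPASI change < 0.5 SD | Loss | SEM/SD, same order |
|---|---|---|---|---|---|
| 0.7 | 0.3 | 0.679 | 0.682 | 0.003 | 0.567, 0.564 |
| 0.7 | 0.5 | 0.647 | 0.667 | 0.020 | 0.594, 0.577 |
| 0.7 | 0.8 | 0.576 | 0.645 | 0.069 | 0.651, 0.596 |
| 0.8 | 0.3 | 0.773 | 0.778 | 0.005 | 0.476, 0.471 |
| 0.8 | 0.5 | 0.729 | 0.756 | 0.027 | 0.520, 0.494 |
| 0.8 | 0.8 | 0.644 | 0.730 | 0.086 | 0.596, 0.520 |

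Over all scenarios the largest loss is 0.727 − 0.632 = 0.095, with a SEM rise of 0.607 − 0.522 = 0.085 SD (reliability 0.8, SD of change 0.8, mean −0.3). With SD of change 0.3, the loss never exceeds 0.012. The choice of set moves the ICC across 0.60 only with reliability 0.7 and SD of change 0.8: 0.57 to 0.58 under the overall sPGA rule, 0.64 to 0.65 under absolute mGPASI change.

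Under these assumptions the overall sPGA rule raised the ICC by at most 0.014 over no selection at all. It removed few of the patients whose genital disease had changed.

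Two limits apply. The simulation did not impose the eligibility minimum on either sPGA. The comparator was the absolute mGPASI set, so the gain from using an unchanged sPGA of Genitalia was not itself simulated.

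**The case against.** **A genital rule already exists.** This stands. The second definition uses mGPASI, and if both rules had to be met together, the weakness of the first would largely be contained. The SAP does not say so, and two ways of defining stability reads more naturally as two sets.

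**sPGA of Genitalia is itself being validated, so it should not define stability.** This holds for its own retest: selecting patients with an unchanged rating would force perfect agreement. It does not hold for the patient-reported scales. SAP 6.20.1.2.5.5.1 already uses sPGA of Genitalia as an anchor for GPSS, GPSIS and SFQ item 2.

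**Eligibility limits the change.** Protocol 5.1 criterion [4], which begins "Have sPGA of Genitalia", requires a rating of at least 3 at both visits. That removes patients who fell below moderate, but movement among 3, 4 and 5 remains possible.

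**A stronger reading of the mGPASI rule.** A reader might infer that, because the bound has no absolute-value bars, every improver passes as stable, however large the improvement. The documents do not support this. SAP 6.1 and Table RHBQ.6.3 define change from baseline only, and the stability rule gives no order of subtraction between screening and baseline. Screening minus baseline would admit large worsening instead. In a definition of stable patients, tied to a hypothesis of unchanged disease status, a change below 0.5 SD is ordinarily read as a magnitude. Where SAP 6.20.1.2.5.4 wants direction at the same cut, it speaks of improvement. Clarification is still worthwhile: if the rule were coded as signed (baseline minus screening), the simulated ICC would differ from the absolute version by between +0.002 and −0.103. With zero mean change, a one-sided mean shift of 0.05 to 0.28 between-patient SD would enter the paired t-test.

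**Conclusion.** The point holds for the first stability rule. It matches genital scales to a whole-body rating although a genital rating is collected at the same two visits. A patient whose genital disease changed before dosing can therefore be classed as stable, which can lower the ICC and raise the SEM.

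A reader might go further and conclude that the ICC and SEM are distorted. The documents do not support that, because they give no information on pre-dose genital change. The range from negligible to about 0.1 on the ICC rests wholly on assumed inputs.

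The practical weight is low. The expected error makes the scales look less reliable, not more. The SEM is supportive only and sits beside a 0.5 SD criterion that does not use the ICC. SAP 6.4 fixes the responder thresholds for itch (3 points) and SFQ item 2 (score 0 or 1), so no primary or major secondary result depends on this analysis.

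**What to change.** Amend SAP 6.20.1.2.5.2 as follows:

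- For GPSS, GPSIS and SFQ item 2, replace the overall sPGA rule with an unchanged sPGA of Genitalia rating at screening and baseline. Keep the overall sPGA set as a sensitivity analysis only.
- For the retest of sPGA of Genitalia, use the mGPASI rule.
- As a clarification, write the mGPASI rule for all scales as absolute change between screening and baseline below 0.5 SD of baseline mGPASI.
- State in SAP 6.20.1.2.5.5.2 which definition's ICC enters the SEM.

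The cost is SAP wording and the matching programming. The data are already collected at Visits 1 and 2.

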8.1.2.2.5. Dermatology Life Quality Index

The DLQI is a simple, patient-administered, 10 question, validated, quality-of-life questionnaire that covers 6 domains: symptoms and feelings, daily activities, leisure, work and school, personal relationships, and treatment. Response categories include "not at all," "a little," "a lot," and "very much," with corresponding scores of 0, 1, 2, and 3, respectively, and "not relevant" responses scored as "0". Totals range from 0 to 30 (less to more impairment). A DLQI total score of 0 to 1 is considered as having no effect on a patient's HRQoL, and a 5-point change from baseline is considered clinically relevant (Basra et al. 2008).

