
 To assess whether 80 mg ixekizumab Q2W is superior to placebo at Week 12 in the treatment of patients with moderate-to-severe genital psoriasis as measured by change in modified Genital Psoriasis Area and Severity Index (mGPASI) 	
 Mean change from baseline in mGPASI at Week 12

Other Secondary Objectives	Other Secondary Endpoints

 • To assess whether 80 mg ixekizumab Q2W is superior to placebo at Week 12 in the treatment of patients with moderate to severe genital psoriasis as measured by the following health outcomes measures: 
 ○ Patient’s Global Assessment of Genital Psoriasis (PatGA-Genital) ○ Dermatology Life Quality Index (DLQI) 
 ▪ Total score ▪ Item 9 ▪ DLQI (0,1) ○ Short form 36 question health survey (SF-36) 
 ▪ physical component summary (PCS) score ▪ mental component summary (MCS) score ▪ 8 domain scores ○ GPSS 
 ▪ Total score ▪ Individual items 	
 ○ The proportion of patients with at least a 2-point improvement from baseline to Week 12 in PatGA-Genital. This analysis will be done among patients who had a baseline score of at least 2. ○ DLQI 
 ▪ Mean change from baseline in DLQI total score at Week 12 ▪ The proportion of patients who with no sexual impairment (i.e. with a DLQI Item 9 score of 0 or 1) at Week 12 ▪ The proportions of patients achieving DLQI (0,1) at Week 12 ○ SF-36 
 ▪ Mean change in SF-36 PCS score and the proportion of patients with at least a 2.5 point improvement at Week 12 ▪ Mean change in SF-36 MCS score and the proportion of patients with at least a 2.5 point improvement at Week 12 ▪ Mean change in SF-36 domain scores at Week 12 ○ Mean change from baseline to Week 12 in 
 ▪ GPSS total score ▪ and individual items

 • Evaluate the incidence of anti-ixekizumab antibodies and its relationship to patient efficacy of ixekizumab at Week 12 	
 • The proportion of patients achieving sPGA of Genitalia (0,1) at Week 12 by treatment emergent anti-drug antibody (TE-ADA) status and by neutralizing anti-drug antibody (NAb) status

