PatGA-Genital	The Patient’s Global Assessment of Genital Psoriasis (PatGA-Genital) is a patient-administered, single-item scale on which patients are asked to rank the severity	PatGA-Genital score	The PatGA-Genital NRS score as reported by the patient. The score ranges from 0 to 5.	Missing if the PatGA-Genital score is missing

Measure	Description	Variable	Derivation	Imputation Approach if Components are Missing
	of their genital psoriasis “today” by circling a number on a 0 to 5 NRS, as follows: from 0 (clear), no genital psoriasis; to 5 (severe).	2 point improvement in PatGA-Genital score	First calculate $\text{Change from baseline} = \text{Observed PatGA Genital score} - \text{Baseline PatGA Genital score}$ If change from baseline is less than or equal to -2, then the patient has experienced a 2-point improvement. If change from baseline is greater than -2, then the patient has not experienced a 2-point improvement.	Missing if the observed or baseline PatGA Genital score is missing
DLQI	The DLQI is a simple, patient-administered, 10 question, validated, quality-of-life questionnaire that covers 6 domains: 
 1. Symptoms and feelings 2. Daily activities 3. Leisure 4. Work and school 5. Personal relationships 6. Treatment Response categories include 0 = not at all 1 = a little 2 = a lot and 3 = very much “not relevant” responses scored as “0”.	DLQI total score	A DLQI total score is calculated by summing all 10 question responses, and has a range of 0 to 30 (less to more impairment). (Finlay and Khan 1994; Basra et al. 2008).	If two or more questions are missing, the total score is missing.
		Change from baseline in DLQI total score	$\text{Change from baseline} = \text{Observed DLQI Total score} - \text{Baseline DLQI Total score}$ A negative change indicates improvement and a positive change indicates deterioration of the condition.	Missing if the observed or baseline DLQI Total score is missing
	DLQI Item 9 asks the following: How much has your skin caused any sexual difficulties?	DLQI Item 9 score	DLQI item 9 score as reported by the patient.	Missing if the DLQI item 9 score is missing

Measure	Description	Variable	Derivation	Imputation Approach if Components are Missing
		No Sexual Impairment	A DLQI Item 9 score of 0 or 1	Missing if the DLQI item 9 score is missing

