	A DLQI total score of 0 to 1 is considered as having no effect on a patient’s Health Related Quality of Life (HRQoL) (Khilji et al. 2002; Hongbo et al. 2005).	DLQI (0,1)	A DLQI (0,1) response is defined as a post-baseline DLQI total score of 0 or 1.	Missing if the DLQI total score is missing
	
DLQI domains
 
 • Symptoms and feelings domain #1. How itchy, sore, painful or stinging has your skin been? #2. How embarrassed or self-conscious have you been because of your skin? • Daily activities #3. How much has your skin interfered with you going shopping or looking after your home or garden? #4. How much has your skin influenced the clothes you wear? • Leisure #5. How much has your skin affected any social or leisure activities? #6. How much has your skin make it difficult for you to do any sport? • Work and school #7A. Has your skin prevented you from working or studying? #7B. If No: how much has your skin been a problem at work or studying? • Personal relationships #8. How much has your skin created problems with your partner or any of 	DLQI Domain scores	
The domain scores are calculated as follows:
 
 • Symptoms and feelings (Sum of Q1 and Q2 scores) • Daily activities (Sum of Q3 and Q4 scores) • Leisure (Sum of Q5 and Q6 scores) • Work and school (Sum of Q7A and Q7B scores) • Personal relationships (Sum of Q8 and Q9 scores) • Treatment (Q10 score) 
A lower value indicates less impairment and a higher value indicates more impairment.
	
If one question in a domain is missing, that domain is missing. Note: #7B could be a valid missing while #7A is not “No.” That is, #7 should be considered as one question.

		Change from baseline in a DLQI domain score	
Change from baseline = Observed DLQI domain score – Baseline DLQI domain score
 
A negative change indicates improvement and a positive change indicates deterioration of the condition.
	Missing if the observed or baseline DLQI domain score is missing

Measure	Description	Variable	Derivation	Imputation Approach if Components are Missing
	your close friends or relatives? #9. How much has your skin caused any sexual difficulties? • Treatment #10. How much of a problem has the treatment for your skin been, for example by making your home messy, or by taking up time?			

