Known-group validity is the extent to which scores from an instrument are different for groups of participants that differ on a relevant clinical or other indicator. Determining known-group validity involves evaluating an instrument in relation to clinical measures of disease status (Stewart et al. 1992; Hays and Revicki 2005). Known-groups validity will be assessed at baseline and Week 12 for: 1) GPSS individual items and total score, 2) GPSIS subscales, 3) SFQ item 2, and 4) sPGA of Genitalia by disease severity. Groups will be defined using several different criteria: 1) using DLQI score categories (score categories: 2-10, 11-20, 21-30); and 2) using PatGA-Genitalia scores (score categories: 0-1, 2-3, 4-5). Additionally, for exploratory purposes, known-groups validity of the SFQ item 2 will be assessed at baseline-and Week 12 using the DLQI sexual difficulties item to define subgroups of patients. Mean scores on the individual items/subscale/total score will be compared for each subgroup using ANCOVA at baseline, and Week 12 controlling for age, sex, and baseline BSA (<10% vs ≥10%).

When the sample size in a subgroup is less than 10% of the analysis population, the subgroup will be repeatedly collapsed with the adjunct subgroups until the sample size in the collapsed subgroup is greater than 10% of the analysis population.

6.20.1.2.5.4. Responsiveness

Responsiveness refers to the extent to which the instrument can detect changes in patients known to have changed in clinical status (Hays and Revicki 2005). The responsiveness of the 1) GPSS item and total score, 2) GPSS subscales, 3) SFQ Item #2, and 4) sPGA of Genitalia will be determined by comparing changes in item/total scores with the changes in selected clinical and health status measures.

The following variables and time points will be used for these analyses:

- **PatGA-Genitalia:** The change scores of the GPSS item and total score from baseline to Week 12 will be correlated with changes in the PatGA-Genitalia at these time points. The change scores of the individual items and GPSS total score from baseline to Week 12 will also be examined using PatGA-Genitalia as an anchor. The means of GPSS and sPGA of Genitalia scores will be compared for patients reporting ≥ 1 point PatGA-Genitalia Improvement, no change, or ≥ 1 worsening in PatGA-Genitalia using ANCOVA adjusted for age, sex, genital psoriasis duration and baseline scores.

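### The DLQI-based known-groups comparison (SAP 6.20.1.2.5.3.2) has no category for totals of 0 or 1, so patients in the plan's own no-effect state are left out of it, mainly at Week 12

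*SAP*

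**What the plan says.** On timing, SAP 6.20.1.2.5.3.2 (Known-Groups Validity) states: "Known-groups validity will be assessed at baseline and Week 12 for" the GPSS items and total, the GPSIS subscales, SFQ Item 2 and sPGA of Genitalia. Two main grouping criteria follow. The first is formed "using DLQI score categories (score categories: 2-10, 11-20, 21-30"). The second is formed "using PatGA-Genitalia scores (score categories: 0-1, 2-3, 4-5"). An exploratory comparison of SFQ Item 2 by the DLQI sexual difficulties item is added. Group means are compared by ANCOVA adjusted for age, sex and baseline BSA category.

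The section also has a rule for small groups: "When the sample size in a subgroup is less than 10% of the analysis population, the subgroup will be repeatedly collapsed with the adjunct subgroups". Merging stops once the combined group exceeds 10%.

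On the DLQI itself, SAP Table RHBQ.6.4 (Section 6.10) says: "A DLQI total score is calculated by summing all 10 question responses, and has a range of 0 to 30". The same table adds: "A DLQI (0,1) response is defined as a post-baseline DLQI total score of 0 or 1". Protocol 8.1.2.2.5 gives the meaning of that state: "A DLQI total score of 0 to 1 is considered as having no effect on a" patient's quality of life. SAP 4.2 lists it among the other secondary endpoints: "The proportions of patients achieving DLQI (0,1) at Week 12".

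**The concern.** A known-groups test asks whether an instrument's scores differ between patients known to differ in severity. It is most informative when the groups span the severity range. Here the lowest DLQI category begins exactly where the plan's no-effect state ends, so the least-affected patients have nowhere to go. The neighbouring PatGA-Genital criterion has no such gap.

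At Week 12 the plan expects some patients to reach DLQI 0-1, because it makes that an endpoint. Leaving them out removes the mildest group and with it the widest DLQI contrast available (0-1 against 21-30). It also leaves programmers to choose, without instruction, between dropping these patients and devising a group for them.

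**Working it through.** **1. Range of the scale.** Ten questions, each scored 0 to 3 (SAP Table RHBQ.6.4). Minimum 10 × 0 = 0; maximum 10 × 3 = 30. This reproduces the stated range of 0 to 30, which contains 31 possible whole-number totals.

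**2. Coverage of the DLQI categories.**

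| Category | Totals covered |
|---|---|
| 2-10 | 9 |
| 11-20 | 10 |
| 21-30 | 10 |
| Sum | 29 |

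31 − 29 = 2 totals are unassigned: 0 and 1. That is exactly the DLQI (0,1) responder set.

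**3. Coverage of the PatGA-Genital categories.** The scale runs from 0 to 5 (six values). The categories 0-1, 2-3 and 4-5 cover 2 + 2 + 2 = 6. None is unassigned.

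**4. Does anything else in the SAP pick up 0 and 1?** The 10% rule merges a defined subgroup with its neighbours; 0-1 is not a defined subgroup, so the rule has nothing to act on. SAP 6.20.1.2.1 names the ITT population for most psychometric analyses and sets no DLQI restriction. No section says that the exclusion is intended.

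**5. How many patients at Week 12?** The documents give no DLQI (0,1) rate, so the rates below are assumptions. With 73 per arm (SAP 5.3), and taking every randomized patient to have a Week 12 DLQI total:

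omitted = 73 × (rate on ixekizumab) + 73 × (rate on placebo)

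| Ixekizumab (assumed) | Placebo (assumed) | Omitted | Share of 146 |
|---|---|---|---|
| 10% | 0% | 7.3 + 0 = 7.3 | 5% |
| 10% | 10% | 7.3 + 7.3 = 14.6 | 10% |
| 30% | 5% | 21.9 + 3.65 = 25.55 | 17.5% |
| 60% | 10% | 43.8 + 7.3 = 51.1 | 35% |

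The range is about 7 to 51 of 146, or 5% to 35%.

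**6. After the change.** With 0-1, 2-10, 11-20 and 21-30, the count is 2 + 9 + 10 + 10 = 31, so every total has a group. The 10% threshold is 0.10 × 146 = 14.6 patients. At the low end of the assumed range (about 7 patients) 0-1 would merge with 2-10; at the high end (about 51) it would stand alone. Either way the patients stay in the comparison.

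**The case against.** A reader might infer that the best-outcome patients vanish from Week 12 known-groups testing altogether. The documents do not support that. Patients with DLQI 0-1 still enter the PatGA-Genital grouping, and the exploratory SFQ Item 2 comparison sets no limit on the DLQI total. The Week 12 correlations in SAP 6.20.1.2.5.3.1, which include GPSS against the DLQI total, also carry no such limit. The responsiveness and responder-definition analyses in SAP 6.20.1.2.5.4 and 6.20.1.2.5.5 use PatGA-Genital, mGPASI and sPGA of Genitalia as anchors, not these DLQI categories. SAP 6.20.1.1 says that no single test settles an instrument's properties. All of this stands, and it confines the point to one grouping criterion.

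A reader might also infer that the omitted patients are mainly ixekizumab responders. That follows only from assumed rates. The DLQI covers skin-related quality of life in general, so a total of 0 or 1 is not the same as sPGA of Genitalia response.

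Three further objections stand. No loss of power or of separation between groups has been calculated, and three ordered groups still make a known-groups test over a narrower range. Few baseline totals of 0-1 are likely, because entry requires an overall sPGA and an sPGA of Genitalia of at least 3 (Protocol 5.1). The psychometric work is an exploratory objective (SAP 4.3).

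It can be said, finally, that the SAP never promises exhaustive categories. That does not remove the gap. If the omission is meant, it is unstated, and it falls exactly on a state that the plan defines and analyses elsewhere.

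**Conclusion.** The point holds for the DLQI-based grouping only. As written, totals of 0 and 1 have no category, and patients with those totals are omitted from that comparison. This conclusion rests on the text and on no assumed rate.

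The size does rest on assumptions: 10-60% DLQI (0,1) on ixekizumab, 0-10% on placebo, 73 per arm and complete Week 12 DLQI data give about 7 to 51 of 146 patients (5-35%). The effect at baseline is probably small.

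The importance is low. The definitions and testing order of the primary and major secondary endpoints (SAP 6.4), the type I error control and the sample size do not depend on this analysis. It is still more than a matter of wording, because the change alters who enters the comparison and restores its mildest group.

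**What to change.** In SAP 6.20.1.2.5.3.2, replace the three DLQI categories with four: 0-1, 2-10, 11-20 and 21-30. Keep the 10% rule as it is; it will merge 0-1 with 2-10 where 0-1 is sparse, as is likely at baseline.

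Two alternatives would also settle the matter. The lowest category could start at 0 (0-10, 11-20, 21-30), which keeps every patient but does not separate the no-effect state. Or, if the exclusion is intended, the SAP could say so, give the reason, and report how many patients are excluded at each time point.

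The cost is one line of SAP text and the matching programming specification. No new data and no change to study conduct are needed.
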